### 7.11.2.2 Analysis of superiority to placebo control

The analysis of superiority will be performed for the primary endpoint separately for the Test treatment versus the Placebo treatment and for the Reference treatment versus the Placebo treatment. Each of these analyses will be performed using an ANCOVA model with change from baseline to Week 4 in the WOMAC Pain Subscale score as outcome, baseline WOMAC Pain Subscale score as covariate and treatment, center and treatment-by-center interaction as factors (mathematical statement of this model is the same as for the equivalence model). If the treatment-by-center interaction factor is not significant at the 0.05 level, the model will be rerun without the interaction term. The model will be fit on data from the Test and Placebo treatment

for analysis of superiority of the Test treatment and separately on data from the Reference and Placebo treatment for analysis of superiority of the Reference treatment. From this model, the least square (LS) mean estimate for each treatment group with the 95% CI will be calculated; further, an estimate of the LS mean difference between the active treatment (Test or Reference) and Placebo with 95% CI and the p-value for test of no difference will be calculated.

Superiority will be established if the mean change from baseline to Week 4 for each active treatment is estimated to be less than, and statistically significantly different from ( $p < 0.05$  for test of no difference) that for the Placebo.

Superiority will be illustrated graphically by a plot including two vertical lines (for Test drug vs. Placebo and Reference Drug vs. Placebo) corresponding to the 95% CI around the Active – Placebo difference with the difference itself indicated by a dot with reference line for 0 difference.

Analysis of superiority will be performed primarily using the mITT population, and additionally on the ITT and PP populations as a sensitivity analysis.

### **7.11.3            Analyses of Secondary Endpoint Outcomes**

The following secondary endpoints will be evaluated in the same way as the primary endpoint, but will be considered as supportive information.

- The change from baseline to Week 2 in total WOMAC Pain Subscale score for the Target Knee.
- The change from baseline to Week 4 in total WOMAC Pain Subscale score for the Target Knee for the subgroup of subjects whose baseline WOMAC pain score is less than or equal to 10.
- The change from baseline to Week 4 in POM VAS score for the Target Knee.

Missing Week 2 assessments will be imputed as follows. In the ITT and mITT analysis, the LOCF rule will be used to impute the score, i.e. the change in the score from the baseline visit to the Early Termination visit, provided it occurs after baseline and within 18 days, (2 weeks + 4 days allowed window) will be carried forward. In the Per Protocol analysis, if a subject

discontinued from the study prior to Week 2 due to treatment failure, the LOCF rule will be used to impute the score as for ITT and mITT analyses. If a subject is missing the Week 2 assessment for any other reason, the subject will be excluded from Per Protocol analysis.

In the analysis of secondary endpoints a 95% CI for the Test/Reference ratio will also be presented in addition to 90% CI.

A descriptive summary by visit will also be created for POM VAS score.

Mean POM VAS score will also be plotted graphically by visit with Mean +/- SD error bars. A separate line will be plotted for each treatment group.

The following secondary endpoints will be summarized descriptively by treatment group:

- Number of days of acetaminophen (paracetamol) consumption during the trial.
- Average daily dose of acetaminophen (paracetamol) during the trial
- Total dose (mg) of acetaminophen (paracetamol) during the trial
- Percentage of patients that used acetaminophen (paracetamol) at least once during the trial

When calculating these endpoints, only days from the day of the first application of the randomized study drug to the day of the last application of the randomized study drug will be counted.

Number of days with any acetaminophen consumption will be counted from the subject's diary.

Average daily dose of acetaminophen will be calculated as follows:

(Sum over all days from the first application of the randomized study drug to the last application of the randomized study drug of [Strength (mg) \* Number of Tablets]) / ([Date of the last application of the randomized study drug] - [Date of the first application of the randomized study drug] + 1)

Total dose (mg) of acetaminophen will be calculated as follows:

Sum over all days from the first application of the randomized study drug to the last application of the randomized study drug of [Strength (mg) \* Number of Tablets])

For these calculations the days without any consumption of acetaminophen will count as zero tablets.

These analyses will be performed on mITT, ITT and PP populations.

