7.14 Rescue medication

Subjects will be permitted to take acetaminophen (paracetamol) tablet as needed during the treatment period. Any use of rescue medication will be recorded by the subject in the subject diary (e.g., Date and time). [REDACTED]

Y

Digitized by [contact]

Digitized by [contact]

Digitized by [contact]

[REDACTED]. Rescue medications will not be permitted within 3 days of the assessments during treatment period. Use of rescue medications by subjects during this period for intolerable pain will require rescheduling the visits in such a way that visits happen after at least 3 days of stopping rescue medication and subjects will be required to inform the site about the rescue

medication use. Site staff will telephonically remind to subjects regarding stop usage of rescue medication before the visit and next visit date. The use of rescue medication will be compared between treatment groups.

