12.3.3 Analysis of Secondary Efficacy Endpoint

1. Mean change in the total WOMAC pain subscale score for the target knee, from baseline to week 2.
2. Mean change in the WOMAC pain subscale score at week 4 for subgroup subjects whose baseline WOMAC pain score less than or equal to 10.
3. Mean change in pain on movement (POM) after 100 meter walk on a Visual Analog Scale (VAS) for target knee from baseline to week 4
4. Average number of days of acetaminophen (paracetamol)consumption during the trial
5. Average dose of acetaminophen (paracetamol)during the trial

For subgroup analysis, similar method as primary analysis will be performed for equivalence and superiority tests. For other secondary endpoints, analysis of covariance (ANCOVA) will be used to compare Test Drug to placebo and RLD to placebo separately. The model will consist of treatment, center and baseline value as covariate. Average duration and dosage of acetaminophen (paracetamol) consumption during the trial will be summarized by descriptive statistics.

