### **Hypotheses of Equivalence and Superiority (Secondary Endpoints)**

The secondary endpoints will be evaluated in the same way as the primary endpoint, but will be considered as supportive information.

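### Rescue days and total rescue dose are not adjusted for time on treatment, and no rescue measure has a between-arm estimate or interval

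*SAP*

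**What the plan says.** **Window.** For the rescue measures, SAP 7.11.3 counts "only days from the day of the first application of the randomized study drug to the day of the last application" of randomized gel.

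**Measures.**
- Rescue days, a listed secondary endpoint in SAP 4, are a raw count: "Number of days with any acetaminophen consumption will be counted from the subject's diary".
- Total dose ("Total dose (mg) of acetaminophen will be calculated as follows") is the sum of strength times tablets over the window, with no divisor.
- Average daily dose, also a listed secondary endpoint, uses the same sum divided by the last application date minus the first plus one (the divisor ends "Date of the first application of the randomized study drug] + 1"). Days without rescue count as zero.
- The percentage of subjects with any use is also given.

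All of these are run on mITT, ITT and PP.

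**Type of analysis.** Four places bear on this:
- Protocol 7.14: "The use of rescue medication will be compared between treatment groups". No method is named.
- Protocol 12.3.3, on the duration and dosage of acetaminophen: "consumption during the trial will be summarized by descriptive statistics".
- SAP 5, with no exception for rescue: "The secondary endpoints will be evaluated in the same way as the primary endpoint, but will be considered as supportive information".
- SAP 7.11.3, which names three WOMAC and VAS endpoints to be handled like the primary and then says of the rescue measures: "The following secondary endpoints will be summarized descriptively by treatment group".

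**The concern.** Acetaminophen is an analgesic that subjects may use throughout treatment except in the three days before Visits 4 and 5. A reader of an equivalence result on WOMAC pain will want to know whether rescue use was similar in Test and Reference.

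A raw count that ends at the last application mixes how often a subject needed rescue with how long that subject stayed. Subjects who leave because the gel is not working may be heavy users, yet their counts are cut short. If more of them leave one arm, that arm's mean rescue days fall for a reason unrelated to lower need. The same applies to total dose.

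Separately, summaries by arm show three means but not the size or precision of any difference. That is little support for a statement that rescue use was similar.

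**Working it through.** **Inputs from the documents.** Planned treatment is 28 days at four applications daily, or 112 applications (SAP 7.12.2). PP requires 75% to 125% of these (SAP 6.6). The superiority size is 363 per arm with 10% dropout overall (SAP 3.2.2). No arm-specific dropout rate and no figure for rescue use is given. Everything else below is assumed for illustration.

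**1. The plan's own dropout figure.** 363 / 0.90 = 403.3, rounded up to 404 per arm; 3 x 404 = 1212. This matches the plan, so 10% is the dropout rate to use.

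**2. One subject.** Assume 1 g of rescue on half of all days.
- 7 days on treatment: 3.5 rescue days, 3,500 mg, 500 mg/day.
- 14 days: 7 rescue days, 7,000 mg, 500 mg/day.
- 28 days: 14 rescue days, 14,000 mg, 500 mg/day.

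The rate of use is the same each time. The two raw measures change fourfold; average daily dose does not change.

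**3. One arm.** Let d be the dropout proportion, f the fraction of 28 days completed before withdrawal, and k the rescue rate of those who leave relative to completers. Then

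observed mean / full-follow-up mean = [(1 - d) + d f k] / [(1 - d) + d k].

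With d = 0.10:
- k = 1, f = 0.75: 0.975 / 1.0 = 0.975. With f = 0.25: 0.925 / 1.0 = 0.925.
- k = 2, f = 0.75: 1.05 / 1.10 = 0.955. With f = 0.25: 0.95 / 1.10 = 0.864.

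Rescue days (and total dose, at a constant dose per rescue day) are understated by 2.5% to 13.6% over this range.

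**4. Two arms with the same daily rate of use (k = 1).** The ratio of mean rescue days is [1 - d1(1 - f)] / [1 - d2(1 - f)].
- Equal dropout and equal f: ratio 1.0, no distortion.
- Assumed 15% versus 5%: 0.8875 / 0.9625 = 0.922 at f = 0.25; 0.925 / 0.975 = 0.949 at f = 0.50; 0.9625 / 0.9875 = 0.975 at f = 0.75. The exposure-adjusted ratio is 1.0 throughout.

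**5. A case where the raw count hides a difference.** Assume completers use rescue on 8 of 28 days and early stoppers on 8 of 10 days, with 15% early stoppers on placebo and 5% on an active gel.
- Raw days: 0.85 x 8 + 0.15 x 8 = 8.0, and 0.95 x 8 + 0.05 x 8 = 8.0.
- Percentage of on-treatment days: 0.85 x 8/28 + 0.15 x 0.8 = 36.29%, and 0.95 x 8/28 + 0.05 x 0.8 = 31.14%. The difference is 5.1 points, ratio 1.165.
- Average daily dose, at an assumed 1 g per rescue day: 363 mg/day and 311 mg/day, the same ratio.

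The days endpoint shows no difference; average daily dose, also planned, shows all of it.

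**6. The equivalence population.** 0.75 x 112 = 84 applications, or 84 / 4 = 21 days at four per day. A subject stopping at Day 10 has about 40 applications (36%) and, on a literal reading of SAP 6.6, is not in PP. At four applications a day, the shortfall for any one included subject is then at most about 7 / 28 = 25%.

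**The case against.** Three stronger readings are tempting, and the documents do not support them.

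**That the plan cannot reveal a difference in rescue use.** It can. Average daily dose has the right divisor, and in step 5 it shows the same 17% relative difference when dose per rescue day is constant. The SAP also reports percentage ever using rescue, duration of exposure by arm, and discontinuations by reason and arm, so unequal truncation would be visible. What stands is narrower: average daily dose measures milligrams rather than frequency, percentage ever using also rises with time observed, and neither has a between-arm estimate.

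**That the equivalence conclusion is undermined.** Equivalence is judged in PP, where the 75% rule removes most early leavers. Protocol 12.2.3 and SAP 6.6 also provide for treatment failures in PP, so some truncation may remain there, but no Test-Reference distortion can be quantified from the documents. Step 5 compares placebo with an active gel, and its rates were chosen to make the raw means equal. There are also safeguards: rescue use in the three days before a visit requires rescheduling, and breach of the rescue rules is a listed deviation that may exclude a subject from PP. Rescue that improves placebo scores works against the superiority claim rather than for it.

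**That the SAP departs from the protocol without saying so.** Protocol 12.3.3 and SAP 7.11.3 both specify descriptive statistics, so the no-changes statement in SAP 8 is accurate on this. A table by arm is a comparison of a weak kind, and SAP 5 can be read as a general sentence that 7.11.3 narrows. What remains is loose wording across four places.

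**Conclusion.** The point holds in limited form. Rescue days and total dose fall mechanically with early withdrawal, and no rescue measure has an estimated difference or interval, despite the statement in Protocol 7.14.

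At 10% dropout the within-arm understatement is 2.5% to 13.6% for the assumed f of 0.25 to 0.75 and k of 1 to 2. Distortion between arms needs dropout, or the timing or rescue use of those who leave, to differ by arm. At an assumed 15% versus 5% with equal daily use it is 2.5% to 7.8%. These sizes are illustrative, and they matter mainly in mITT and ITT. The average daily dose result takes the formula printed in SAP 7.11.3 as the operative one.

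Severity is minor. The rescue endpoints are supportive and do not enter the three tests that decide success. This is a cheap improvement, not a defect in the primary analysis.

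**What to change.** In SAP 7.11.3:
- Report rescue days as a percentage of on-treatment days: days with any acetaminophen divided by (last application date - first application date + 1), the divisor already used for average daily dose.
- For this percentage and for average daily dose, give Test-Reference differences with 90% CIs and each active gel minus placebo with 95% CIs, in PP and mITT. Label them supportive. No margin is set, so the 90% CI describes precision and is not an equivalence test.
- Keep raw rescue days and total dose as descriptive rows.

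Align Protocol 7.14, Protocol 12.3.3, SAP 5 and SAP 7.11.3 so that they state the same analysis for rescue use.

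The cost is some SAP wording and a few table rows from data already collected; the decision rule and trial conduct do not change. There are two limits. Percentages are noisier for subjects with short exposure, and rescue taken after the last application stays uncounted because the window is unchanged.

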#### **7.11.4 Subgroup analyses**

The following subgroups will be considered:

1. Subjects with baseline Kellgren-Lawrence grade 1 or 2;
2. Subjects with baseline Kellgren-Lawrence grade 3.

The analyses of the primary endpoint described above will be repeated by subgroup. This will be an exploratory analysis and inference about equivalence and superiority of the study drug on the subgroups will not be drawn.

#### **7.11.5 Forest Plot**

A forest plot representing Test/Reference ration with 90% CI will be presented for all endpoints and subgroups for the PP, mITT and ITT populations:

1. Change from Baseline to Week 4 in WOMAC Pain Subscale Score:
  - a. All subjects
  - b. Subjects with Baseline WOMAC Pain Subscale Score <= 10
  - c. Subjects with Baseline Kellgren-Lawrence Grade 1-2
  - d. Subjects with Baseline Kellgren-Lawrence Grade 3
2. Change from Baseline to Week 2 in WOMAC Pain Subscale Score: for all subjects
3. Change from Baseline to Week 4 in POM VAS Score: for all subjects

Each CI will be represented by a horizontal line with a dot marking the ratio itself. Reference lines will be drawn to represent ratios of 100%, 80% and 125%

### **7.12 Safety Analyses**

#### **7.12.1 Adverse Events**

Adverse Events will be coded using the Medical Dictionary of Regulatory Activities (MedDRA version 20.0) AE coding system for purposes of summarization.

An AE will be considered as treatment-emergent if the time of onset is after the time of the first randomized study drug administration or if it increased in severity during the study period. AEs with unknown start dates will be counted as treatment-emergent unless the AE resolution date is prior to the study drug start date. If the start date is partially missing, AE will be considered treatment-emergent unless the known part of the start date or the end date rules out that it occurred after the start of the study drug. See [appendix 11.3](#) for more details on handing of partial dates.

A TEAE is defined as treatment-related if it is recorded as definitely, probably or possibly related to the study medication at the eCRF. In case the relatedness was not assessed, the most conservative result – related will be chosen for the analysis.

An overall summary will include, by treatment group and overall, the number and percentage of subjects reporting at least one TEAE and subjects discontinuing the study drug due to TEAE, as well as counts of AEs by severity, relationship, count of serious AEs and deaths.

A summary of the frequencies (number and percentage) of subjects with TEAEs and counts of TEAEs will be presented by system organ class and preferred term. Similar summaries will be created for serious TEAEs, TEAEs leading to treatment discontinuation and for TEAEs leading to death (if any).

Similar summaries of non treatment-emergent AEs and serious non treatment-emergent AEs by system organ class and preferred term will be created for the run-in population.

Additionally number and percentage of subjects with TEAE will be presented by preferred term only in the descending order of frequency for TEAEs experienced by >1% of subjects.

TEAEs will also be summarized by system organ class, preferred term and maximum severity as well as by system organ class, preferred term and closest relationship to the study drug (not related or related).

A subject experiencing the same AE multiple times will only be counted once for that preferred term. Similarly, if a subject experiences multiple AEs within the same system organ class that subject will be counted only once in that system organ class. In summaries by severity or by relationship, if a subject has the same AE on multiple occasions, the highest severity, and the closest relationship to study drug, respectively, will be used.

All information pertaining to adverse events noted during the study will be listed by subject, detailing verbatim, preferred term, system organ class, start date, stop date, severity, outcome, action taken and causal relationship to the study drug.

#### **7.12.1.1 Application Site Reactions**

Application site reactions are a subset of treatment-emergent adverse events. They will be identified by specific preferred terms. The list of preferred terms for application site reactions will be finalized prior to the database lock.

Number and percent of subjects and number of events will be summarized for application site reactions by preferred term and treatment. Application site reactions also will be listed.

#### **7.12.2 Exposure to Product**

The subjects will be instructed to use the diary to document all doses taken by checking the yes or no box for the appropriate date.

Study drug compliance will be defined as

[Actual number of applications] / [Planned number of applications] \* 100%

where:

- Actual number of applications will be calculated from the subject diary as the number of gel application in the treatment period dosing log.
- Planned number of applications is 112 (28 days, 4 times daily).

Subjects will be considered treatment compliant if they apply at least 75% and not more than 125% of doses.

Duration of exposure will be defined as [Date of last study drug application] – [Date of first study drug application] + 1;

Compliance, actual number of applications and duration of exposure will be summarized descriptively by treatment group for the safety population.

Duration of exposure to the placebo treatment in the run-in period will also be summarized descriptively for the run-in population.

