7.10 Treatment Compliance

A Subject Diary will be provided to all subjects where it is required to document the date and time of application of the medication. In the subject diary, subjects will also note of any adverse event observed, date and time of rescue medication administration and any concomitant medication taken or changed.

Compliance will be determined from the subject diary, which the subject will be trained and instructed to use to record all doses, as well as all missed doses. The number of missed and additional doses will be captured on the compliance page of the eCRF.

The used study medication tubes will be returned to the study site at appropriate visits or early termination or as applicable.

Subjects who are not compliant with application will be re-c counseled during the study visits.

Subjects who will take less than 75% (<84 applications) of total study drug during the study will be considered non-compliant and discontinued from the study. Subjects who will take more than 125% (>140 applications) of study drug are also considered non-compliant and the same subjects will not be considered for the Per-protocol (PP) population.

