## **6.6 Per Protocol Population (PP Population)**

The Per Protocol (PP) population includes all mITT subjects who:

- met all inclusion/exclusion criteria
- apply 75% to 125% (both inclusive) of the scheduled applications of the assigned product
- return for the 4 week evaluation of WOMAC Pain Subscale score within the visit window (+/- 4 days; i.e., study Day 24-32) or discontinue from the study due to treatment failure (included as treatment failures)
- have no major protocol deviations impacting the primary efficacy outcome measure.

These major protocol deviations are described in [section 7.9](#). The list of protocol deviations which lead to exclusion of subjects from the PP population will be finalized at the Blind Data Review (BDR) meeting to be held prior to database lock.

This population will be used for testing the clinical equivalence.

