### **7.1.1 Derivation of dates**

The start of the run-in period will be taken from the “Run-In Period Day 1 Date” field collected at the “Run-In Period Dosing Log” CRF page.

The end of the run-in period will be derived as the date corresponding to the maximum day recorded at the “Run-In Period Dosing Log” CRF page when gel was applied.

The start of the treatment period, i.e. the date of the first application of the randomized study drug, will be taken from the “Treatment Period Day 1 Date” field collected at the “Treatment Period Dosing Log” CRF page.

For subjects who started the treatment period, the end of the treatment period, i.e. the date of the last application of the randomized study drug, will be taken from the “Date of Last Gel Application” field collected at the “End of Study” CRF page. It must correspond to the maximum day recorded at the “Treatment Period Dosing Log” CRF page when gel was applied or the maximum date recorded at the “Treatment Period Dosing Log (Extended)” CRF page, if any.

Study days will be defined relative to the start of the treatment period. For dates after the start of the treatment period:

Study Day = Date of Assessment – Start of the treatment period + 1

For dates prior to the start of the treatment period:

Study Day = Date of Assessment – Start of the treatment period

All dates will be displayed in DDMMYY format.

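### The fixed denominator of 112 applications makes the 75% per-protocol compliance limit stricter for subjects whose Week 4 visit falls early in the allowed window

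*SAP*

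**What the plan says.** SAP 7.12.2 defines compliance as actual over planned applications. The denominator is the same for every subject: "Planned number of applications is 112 (28 days, 4 times daily". The numerator has no stated cut-off date: "Actual number of applications will be calculated from the subject diary as the number of gel application in the treatment period dosing log".

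Protocol 7.10 gives the limits as counts: "Subjects who will take less than 75% (<84 applications) of total study drug during the study will be considered non-compliant", and "Subjects who will take more than 125% (>140 applications) of study drug are also considered non-compliant". SAP 6.6 makes the same limits a condition for the per-protocol (PP) population, whose members must "apply 75% to 125% (both inclusive) of the scheduled applications of the assigned product". SAP 5 and 7.11.2.1 use that population for the equivalence decision.

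SAP 6.6 also requires that subjects "return for the 4 week evaluation of WOMAC Pain Subscale score within the visit window", given as plus or minus "4 days; i.e., study Day 24-32". Gel starts on Day 1 (SAP 3.1) and unused product is collected at Visit 5 (Protocol 10.3.3). The regimen is described as four applications a day over 4 weeks (Protocol 4.1, SAP 3.1), yet SAP 7.1.1 also refers to a form named "Treatment Period Dosing Log (Extended" for later dates. Neither document adjusts the planned number to the actual visit day.

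**The concern.** The visit window lets the time available for dosing vary, but the denominator does not follow it. A subject called in on Day 24 hands back the gel then and cannot make the applications of the remaining days, which are nevertheless counted as missed. The nominal 75% limit is then a different adherence standard depending on a visit date that the plan itself allows.

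At stake is who enters the PP population. Subjects who used the gel as directed, and have a valid Week 4 score, could be excluded from the equivalence test because of scheduling.

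**Working it through.** **Inputs.** Four applications a day; 112 planned (SAP 7.12.2); limits of 75% and 125% (SAP 6.6); Visit 5 on Study Day 24 to 32 (SAP 6.6); first application day is Study Day 1 (SAP 7.1.1).

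**The plan's own figures.** 28 × 4 = 112; 0.75 × 112 = 84; 1.25 × 112 = 140. All reproduce, and the protocol and SAP agree.

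**Adherence implied by the limits.** Possible applications are 4 × (visit day − 1) if the last dose is the day before the visit, or 4 × visit day if the visit day is fully dosed. The documents do not say which, so both are shown. Implied limits are 84 and 140 divided by the possible number.

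| Visit 5 | Possible applications | 84 is | 140 is |
|---|---|---|---|
| Day 24 | 92 or 96 | 91.3% or 87.5% | 152.2% or 145.8% |
| Day 26 | 100 or 104 | 84.0% or 80.8% | 140.0% or 134.6% |
| Day 28 | 108 or 112 | 77.8% or 75.0% | 129.6% or 125.0% |
| Day 32, gel stops at Day 28 | 112 | 75.0% | 125.0% |
| Day 32, gel continues to the visit and is counted | 124 or 128 | 67.7% or 65.6% | 112.9% or 109.4% |

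**Example.** A Day 24 subject with 83 of 92 possible applications has adherence 83/92 = 90.2%, but scores 83/112 = 74.1% and is excluded. If the visit day was available for dosing, adherence is 83/96 = 86.5%, with the same exclusion. A fully adherent Day 24 subject scores 92/112 = 82.1% or 96/112 = 85.7% and passes.

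**How many subjects.** The documents give no distribution of visit days or adherence, so these are assumptions: visit days uniform or triangular over Days 24-32, and beta-distributed adherence with mean and SD of 85% and 12%, 90% and 10%, or 95% and 6%. Counts were drawn binomially, with 400,000 draws per setting. The share of completers with at least 75% of their possible applications but fewer than 84 in total is about 2% to 11% if the last dose is the day before the visit, and about 1% to 7% if the visit day is dosed. The result is the same whether or not gel stops at Day 28, because the error arises only where fewer than 112 applications are possible.

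**Effect on PP numbers.** 404 × 0.90 = 363.6 per arm after the planned 10% dropout. Losing a further 11% leaves 363.6 × 0.89 = 323.6, still above the 261 per arm stated for equivalence, before any other PP exclusions.

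**The case against.** The strongest defence is that a minimum total exposure is a legitimate PP criterion, is prespecified, and is stated identically in both documents. It stands this far: there is no contradiction between protocol and SAP, and the rule can be applied as written. It does not remove the problem. SAP 6.6 expresses the criterion as a percentage of scheduled applications, which reads as adherence, and its own window admits the early visits that are then penalised.

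Day 24 is the extreme of the window, and near Day 28 the distortion is small. That is true and is reflected in the range above. Equivalence is also analysed in ITT and mITT (SAP 7.11.2.1), where the limit does not apply, but those are sensitivity analyses. The blind data review finalises the list of excluding deviations, but the 75%-125% condition stands separately in SAP 6.6, so the review does not clearly have authority to readmit these subjects.

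A reader might infer three stronger points, none of which the documents support:

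- **That late-visit subjects need only about 66%-68% adherence.** This holds only if application continues to a Day 32 visit and those entries are counted. The regimen is stated as 4 weeks; the extended log shows that later applications can be recorded, not that they are scheduled. If gel stops at Day 28 the limit is 75%.
- **That the rule keeps subjects who are off drug.** A subject who stops on Day 21 after 84 applications and is seen on Day 32 does score 84/112 = 75%. That is a matter of early stopping. Even a denominator tied to the visit gives 84/108 = 78% on Day 28 and keeps the subject.
- **That the ratio is pulled toward 1.** Take the means in SAP 3.2 (5.85 active, 4.68 placebo) and a test product at the margin, 0.80 × 5.85 = 4.68. If 2% of both active arms had no drug effect at all, the reference mean is 0.98 × 5.85 + 0.02 × 4.68 = 5.83 and the ratio moves from 0.800 to 0.803. The effect is negligible.

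**Conclusion.** The early-visit problem is real and modest. For an in-window Week 4 visit before Day 28, the nominal 75% limit demands more than 75% adherence, reaching 87.5%-91.3% on Day 24. This does not depend on what happens after Day 28. The estimate of about 1%-11% of completers rests on the assumed distributions and would shrink if most visits cluster at Day 28. The likely cost is PP subjects and an uneven entry standard. Bias in the test/reference ratio is not demonstrated, and the planned numbers leave room for the loss. What happens to the limit for late visits cannot be settled from the documents, because they leave both the end of application and the use of extended-log entries unclear.

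**What to change.** In SAP 7.12.2, for subjects with an in-window Week 4 assessment, define planned applications as 4 × the number of scheduled dosing days from the first randomized application to that assessment, capped at the end of the scheduled dosing period (28 days as written). Count actual applications over the same days, state whether the visit day is included, and apply the existing 75%-125% limits to that ratio. The limits for a Day 24 visit become 69 to 115 of 92, or 72 to 120 of 96. Keep 112 for the descriptive exposure table.

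The cap matters. Without it, a subject who applied 92 of 112 (82%) by Day 28 and was seen on Day 32 would score 92/124 = 74% and be wrongly excluded.

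Reconcile the 4-week regimen with the extended dosing log, and state whether extended entries enter the numerator. Which dosing period applies is for the sponsor to settle; the cap then follows it.

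The cost is small: one derivation from dates already collected, a clarification of the fixed counts of 84 and 140 in Protocol 7.10, and an entry in SAP 8, which now reports no changes from the protocol. PP membership changes slightly, so the rule must be fixed before unblinding, and preferably before the blind data review.
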